**Smith+Nephew**

**Clinical Protocol - Device**

**Pre-Registration Clinical  
Study**

Study Number:  
CT1705POB  
Version:9.0 04Aug2021  
Page: 78 of 221

**Smith+Nephew**

**Clinical Protocol - Device**

██████████ **Pre-Registration Clinical**  
**Study**

Study Number:  
CT1705POB  
Version:9.0 04Aug2021  
Page: 79 of 221

**Smith+Nephew**

**Clinical Protocol - Device**

**Pre-Registration Clinical  
Study**

Study Number:  
CT1705POB  
Version:9.0 04Aug2021  
Page: 80 of 221

## **9.3 Health Economics/Quality of Life**

Specific validated Quality of Life questionnaires will not be collected for this study. However, assessment of acceptability of the therapies will be made by specific targeted questions to the clinician and subject as described in section 9.1.2 above.

## **10 STATISTICAL DESIGN**

A Statistical Analysis Plan (SAP) will be written and finalized prior to database lock. The following is a brief description of the analyses to be described in this plan. The SAP will be more detailed and account for all analyses. All analyses will be conducted with statistical software SAS Version 9.4 or later.

### **10.1 General**

The subject data will be described and summarised using the baseline demographic and medical variables which include but are not limited to age, gender, ethnicity, medical and medication history, diagnostic factors as well as study process variables (e.g. AE and withdrawal(s). Summary statistics will be given according to the nature of the variable, continuous or categorical. For categorical variables, the number of observations, mean, standard deviation, median, minimum, and maximum will be presented, while for categorical variables the number of observations, frequency, and percentages will be reported. All summaries and analyses will be presented separately for each of the two cohorts of specialties recruited within the study: orthopaedics (closed knee incisions e.g. after Total Knee Arthroplasty), and Abdominal surgery (closed abdominal surgical incisions). No data will be combined between the two specialties.

Primary, secondary, and exploratory outcome variables and derived variables will also be summarised accordingly separately by specialty. Parametric statistical tests will be used if

**CONFIDENTIAL AND PROPRIETARY**

This document contains information that is confidential and proprietary to Smith & Nephew PLC and Smith & Nephew, Inc. and is intended for use only by Smith & Nephew and its manufacturer. It shall not be reproduced or copied in whole or in part, nor shall the contents be disclosed by any means without prior written permission from Smith & Nephew, nor shall anyone make any use of it that is contrary to the expressed or implied wishes of Smith & Nephew.

TMP-[REDACTED] - [REDACTED] - [REDACTED]

**Clinical Protocol - Device****Pre-Registration Clinical  
Study**

Study Number:  
CT1705POB  
Version:9.0 04Aug2021  
Page: 82 of 221

the data is normally distributed and corresponding non-parametric tests will be considered if the data is not. Where necessary, suitable regression techniques will be used to adjust for confounding since the study is non-randomised. The results will be reported at 5% significance level and where appropriate 95% confidence intervals (CI) will be given.

## 10.2 Analysis Populations

- Safety Population (SAF), including all subjects who have received the study device.
- Full analysis set population (FAS), following ITT principle including all subjects recruited into the study.
- Per-Protocol Population 1 (PP), including all subjects in the full analysis set who have no significant protocol deviations and met the inclusion/exclusion criteria.

Statistical analysis will be performed using each of the subject populations as follows. Analysis of the primary, secondary and exploratory performance objectives will be performed separately using both the Full Analysis Set and the Per Protocol Population. All safety analyses will utilize the Safety Population, separately for each specialty.

Subsets of the above populations will be used for secondary analyses where appropriate to analyse only those subjects in the abdominal group who were recruited post-interim analysis and followed version 8.0 of the protocol. These subset populations will be labelled with the prefix "s-" so it is clear, for example the subset of the full analysis set will be labelled s-FAS etc.

## 10.3 Baseline Data

The subjects will be described and summarised using the baseline demographic and medical variables which include but are not limited to age, gender, ethnicity, medical and medication history, diagnostic factors. Summary statistics will be given according to the nature of the variable, continuous or categorical. For categorical variables, the number of observations,

## CONFIDENTIAL AND PROPRIETARY

This document contains information that is confidential and proprietary to Smith & Nephew PLC and Smith & Nephew, Inc. and is intended for use only by Smith & Nephew and its manufacturer. It shall not be reproduced or copied in whole or in part, nor shall the contents be disclosed by any means without prior written permission from Smith & Nephew, nor shall anyone make any use of it that is contrary to the expressed or implied wishes of Smith & Nephew.

**Clinical Protocol - Device****Pre-Registration Clinical  
Study**

Study Number:  
CT1705POB  
Version:9.0 04Aug2021  
Page: 83 of 221

mean, standard deviation, median, minimum, and maximum will be presented, while for categorical variables the number of observations, frequency, and percentages will be reported.

## **10.4 Efficacy Analysis**

The study is non-comparative and non-randomised, the impact of confounding on the measures of performance may be expected and will be evaluated through descriptive analysis of selected baseline and demographic variables and fitting of appropriate models on selected outcomes presented separately for each specialty.

The primary analysis of the following endpoints will be done using FAS and PP analysis populations. However, an additional analysis will also be carried out on a subset of these populations (s-FAS and s-PP) which includes only subjects who were recruited post-interim analysis and followed protocol version 8.0.

### **10.4.1 Analysis of Primary Endpoint(s)**

- Negative Pressure maintenance at nominal 80mmHg

The following hypotheses will be tested to establish equivalence of the [REDACTED] compared to the internally derived value, with equivalence margin,  $\delta_1 > 0$ , for each specialty cohort:

$$H_0: |\mu - \mu_0| \geq \delta_1$$

$$H_a: |\mu - \mu_0| < \delta_1$$

In the stated hypotheses,  $\mu$  represents the assumed mean operating pressure (80.2 mmHg) and  $\mu_0$  represents the mean [REDACTED] operating pressure. The equivalence limit  $\delta_1 = 7\text{mmHg}$  was chosen as a conservative non-clinically significant difference assuming that the difference is actually 0. The hypothesis will be tested by two-one-sided t-test (TOST)

## CONFIDENTIAL AND PROPRIETARY

This document contains information that is confidential and proprietary to Smith & Nephew PLC and Smith & Nephew, Inc. and is intended for use only by Smith & Nephew and its manufacturer. It shall not be reproduced or copied in whole or in part, nor shall the contents be disclosed by any means without prior written permission from Smith & Nephew, nor shall anyone make any use of it that is contrary to the expressed or implied wishes of Smith & Nephew.

[REDACTED] - [REDACTED] - [REDACTED]

Smith+Nephew

**Clinical Protocol - Device****Pre-Registration Clinical  
Study**

Study Number:  
CT1705POB  
Version: 9.0 04Aug2021  
Page: 84 of 221

at the alpha level of 0.025 (one-sided), separately for each specialty. If the null hypothesis is rejected, equivalence will be confirmed.

The corresponding 95% CI for each cohort will also be presented.

- Dressing wear time in days as assessed through a combination of data from [REDACTED] and CRF recorded data of any unplanned dressing change.

The following hypotheses will be tested, for each specialty separately, to establish that the dressing wear time of the [REDACTED] pump system is strictly no worse (lower) than the literature derived value:

$$H_0: \mu - \mu_0 \leq 0$$

$$H_a: \mu - \mu_0 > 0$$

In the stated hypothesis,  $\mu$  represents the mean [REDACTED] dressing wear time in days and  $\mu_0$  represents the literature derived value (4.6 days). A one sided (one sample) t-test with alpha = 0.025 will be used to evaluate the hypothesis for each specialty, the corresponding 95% CIs will also be presented. A binary variable indicating  $<7$  /  $\geq 7$  days wear time (denoted by 0/1) will also be used and the proportion of dressings with a wear time  $\geq 7$  days will be reported as a percentage along with corresponding 95% confidence interval, for each specialty cohort. If necessary and if data allows, important associated factors will be adjusted for in a logistic model.

- Exudate management assessed by no occurrence of exudate leaks as assessed by reported clinical data on any exudate leakage observed through a dressing or around the borders during the dressing wearing period resulting or not, in an unplanned dressing change.

A binary variable for the non-leakage and leakage will be used and the proportion of reported/identified leaks will be presented as a frequency together with a percentage and a

## **Clinical Protocol - Device**

### **Pre-Registration Clinical Study**

Study Number:  
CT1705POB  
Version:9.0 04Aug2021  
Page: 85 of 221

95% CI separately for each specialty. For each specialty, the non-leakage proportion for the study will be tested using the Exact test to establish if it is different from the literature derived value of 85% projected. Further, the resulting lower limit of 95% CI for each specialty will be evaluated to establish if it excludes values of 65% and below.

Composite Clinical Success (CCS) defined as a binary variable (1/0) (1 if all three of the following are true and 0 if at least one of the three is false):

- A. Average negative pressure within therapeutic range (-100mmHg to -60mmHg)
- B. Dressing wear time is 7 days
- C. No exudate leakage

The Composite Clinical Success (CCS) will be reported as a count and percentage with a 95% CI separately for each specialty.

A logistic model will be used to evaluate the adjusted and the un-adjusted models for the CCS primary outcome variable for each specialty, separately. The variables considered important and to be included in the final model are Age, Diabetic status and the presence of any other co-morbidity as a binary variable. All other baseline and medical factors collected at baseline will be evaluated for importance in adjusted models and only those statistically significant in an un-adjusted model will be considered in the final model.

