## **8.4 Study Endpoints**

### **8.4.1 Primary Endpoint**

Functional clinical performance of [REDACTED] NPWT system over 7 days therapy to be assessed using a composite endpoint including the following components:

- Negative Pressure maintenance at nominal 80 mmHg [REDACTED]  
[REDACTED].
- Dressing wear time (7 days) as assessed through a combination of [REDACTED]  
[REDACTED] and CRF recorded data of any unplanned dressing change.
- Exudate management assessed by no occurrence of exudate leaks as assessed through clinical data on any leakage of exudate through a dressing or around

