## **11 SAMPLE SIZE JUSTIFICATION**

### **11.1 Sample Size Justification Pre-Interim Analysis**

The sample size is justified based on the proposed three primary outcome variables of nominal pressure of 80mmHg, Dressing wear time in days and exudate management based

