**CONFIDENTIAL AND PROPRIETARY**

This document contains information that is confidential and proprietary to Smith & Nephew PLC and Smith & Nephew, Inc. and is intended for use only by Smith & Nephew and its manufacturer. It shall not be reproduced or copied in whole or in part, nor shall the contents be disclosed by any means without prior written permission from Smith & Nephew, nor shall anyone make any use of it that is contrary to the expressed or implied wishes of Smith & Nephew.

---

**Clinical Protocol - Device****Pre-Registration Clinical  
Study**

Study Number:  
CT1705POB  
Version:9.0 04Aug2021  
Page: 89 of 221

on incidence of exudate leakage. Each of the three hypotheses will be tested separately for each specialty cohort.

For the nominal pressure the sample size is based on analysis to test equivalence of negative pressure delivery against the reference value of 80.2mmHg. Previous data extracted from the PICO 7 system were found to be distributed with a SD=14.8. For purposes of sample size calculation, the a priori assumption is that the [REDACTED] system will have a similar operating pressure to PICO 7, and therefore similar variability in pressure delivery is assumed. The following hypotheses will be tested to establish the equivalence in mean operating pressure of [REDACTED] system over 7 days compared to the reference value for PICO 7 (80.2 mmHg) with equivalence margin,  $\delta_1$ :

$$H_0: |\mu - \mu_0| \geq \delta_1$$

$$H_a: |\mu - \mu_0| < \delta_1$$

In the stated hypotheses,  $\mu$  represents the mean operating pressure of [REDACTED] system and  $\mu_0$  represents , the reference value relating to the mean operating pressure of PICO 7 (=80.2mmHg, SD=14.8). The equivalence margin,  $\delta_1 = 7$  mmHg was chosen as a conservative non-clinically significant difference for operating pressure assuming the difference is actually 0. The hypothesis will be tested, separately for each specialty cohort by a two-sided t-test (TOST) at the alpha level of 0.025 (one-sided). If the null hypothesis is rejected, clinical equivalence in terms of pressure delivery will be confirmed.

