**CONFIDENTIAL AND PROPRIETARY**

This document contains information that is confidential and proprietary to Smith & Nephew PLC and Smith & Nephew, Inc. and is intended for use only by Smith & Nephew and its manufacturer. It shall not be reproduced or copied in whole or in part, nor shall the contents be disclosed by any means without prior written permission from Smith & Nephew, nor shall anyone make any use of it that is contrary to the expressed or implied wishes of Smith & Nephew.

[REDACTED] - [REDACTED] - [REDACTED]

**Clinical Protocol - Device****Pre-Registration Clinical  
Study**

Study Number:  
CT1705POB  
Version:9.0 04Aug2021  
Page: 92 of 221

The 2nd phase of the study (post-interim analysis) will be powered according to previous sample size. However, as no further subjects will be recruited for the orthopaedic surgery group, all 44 subjects recruited will be in the abdominal indication group. This will increase the total number of abdominal incisions to 66 (22 recruited following the protocol v7.0 and 44 following v8.0 of the protocol). This ensures that the primary endpoint is sufficiently powered for both the primary analysis of the abdominal data for all subjects as well as for a secondary analysis to be done on the data from those recruited according to protocol v8.0 only.

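### Section 11.2 calls the primary endpoint adequately powered at both 66 and 44 subjects, but the composite has no benchmark or power calculation, and at 44 the pressure equivalence test alone has 73% power (62% with the planned 38 evaluable), not 80%

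*Combined protocol and SAP*

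**What the plan says.** Section 8.4.1 defines the primary endpoint as functional performance over 7 days, "to be assessed using a composite endpoint including the following components": negative pressure, wear time and exudate management. Section 10.4.1 turns this into a binary Composite Clinical Success (CCS) per subject: average pressure between -100 and -60 mmHg, 7 days of wear, and no exudate leak. Two analyses of CCS are given:

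- Estimation: "The Composite Clinical Success (CCS) will be reported as a count and percentage with a 95% CI separately for each specialty".
- Covariate modelling, in which age, diabetic status and other co-morbidity always enter: "A logistic model will be used to evaluate the adjusted and the un-adjusted models for the CCS primary outcome variable".

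Neither compares CCS with a target.

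Section 11.1 takes a different basis: "The sample size is justified based on the proposed three primary outcome variables", and "Each of the three hypotheses will be tested separately for each specialty cohort". The pressure calculation drives the number: 38 subjects for 80% power, raised to 44 for 15% loss.

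Section 11.2 adds the second phase: "This will increase the total number of abdominal incisions to 66 (22 recruited following the protocol v7.0 and 44 following v8.0". From these two sample sizes it draws its conclusion about power: "This ensures that the primary endpoint is sufficiently powered for both the primary analysis of the abdominal data for all subjects". It extends the claim to the secondary analysis of the v8.0 subjects alone. The Sample Size entry of the synopsis repeats this.

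**The concern.** The power sentence concerns the primary endpoint, which the plan names as a composite, yet no calculation in the document concerns that composite. Its power cannot be computed, because there is no null value or performance goal to compute it against.

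Power for the components does not carry over to CCS. The wear-time test asks whether the mean exceeds 4.6 days, whereas CCS requires 7 days in each subject. The pressure test concerns a group mean within 7 mmHg of 80.2, whereas CCS looks at each subject's own average against a 40 mmHg range. All three component criteria could be met alongside a modest CCS.

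Section 4.3 says that the data will support CE marking. A reader will take the sentence as assurance about the main performance claim, in the full abdominal set and again in the v8.0 subset. If that assurance is wrong for the subset, an inconclusive equivalence result there could be read as evidence about the device when it may only reflect the size of the set.

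**Working it through.** **Inputs (Sections 10.4.1 and 11.1).** Pressure: reference 80.2 mmHg, SD 14.8, margin 7, true difference 0, TOST at one-sided alpha 0.025. Exudate: true non-leak rate 85%, lower limit of the 95% CI to exceed 65%, CI method not named. Wear time: 7 against 4.6 days, SD 2.25, one-sided t-test at 0.025. Loss: 15%.

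**Step 1: the plan's 38.** For a one-sample TOST with true difference 0, the normal approximation is power = 2Φ(δ√n/σ − 1.96) − 1.

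- n = 38: 7 × √38 / 14.8 = 2.916; 2.916 − 1.96 = 0.956; 2Φ(0.956) − 1 = 66.1%.
- n = 44: 7 × √44 / 14.8 = 3.137; 3.137 − 1.96 = 1.177; 2Φ(1.177) − 1 = 76.1%.

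The exact version replaces 1.96 by the t quantile and integrates over the chi-square distribution of the sample variance:

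| Evaluable n | Exact TOST power |
|---|---|
| 38 | 62.1% |
| 44 | 73.2% |
| 48 | 78.8% |
| 49 | 80.1% |
| 56 | 87.1% |
| 66 | 93.2% |

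So 38 does not give 80%; 49 evaluable are needed. An ordinary two-sided one-sample t-test to detect a 7 mmHg difference does return 38 (79.9% at 37, 81.0% at 38), but that is not the equivalence test specified. TOST at one-sided 0.05 would need 40 (77.6% at 38), and that is not the stated alpha.

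**Step 2: the other components.** Exudate, by exact binomial probability with a Clopper-Pearson interval:

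| n | Non-leaks needed | Power |
|---|---|---|
| 38 | 31 | 79.9% |
| 44 | 36 | 79.4% |
| 56 | 44 | 93.2% |
| 66 | 51 | 96.8% |

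With a Wilson or Wald interval at 44, 35 non-leaks suffice and power is 88.6%. Wear time at 44: noncentrality (7 − 4.6) / 2.25 × √44 = 7.08, power above 99.9%; it is also above 99.9% at 38.

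**Step 3: all three together.** The plan states no such rule, so this is illustrative. Wear time contributes almost nothing, and the product assumes independence.

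- n = 44: 0.7315 × 0.7941 = 58.1% (Wilson or Wald: 0.7315 × 0.8864 = 64.8%).
- n = 44 without independence, exact CI: from 0.7315 + 0.7941 − 1 = 52.6% up to the smaller component, 73.2%.
- n = 38: 0.6207 × 0.7986 = 49.6%.
- n = 66: 0.932 × 0.9675 = 90.2%; without independence, 90% to 93%.
- n = 56 (66 × 0.85): 0.8707 × 0.9318 = 81.1%; without independence, 80% to 87%.

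**Step 4: precision of CCS.** The plan gives no expected CCS. If it were near 70%, the exact 95% intervals would be 57% to 80% for 46/66 and 55% to 83% for 31/44, or about 12 and 14 points either side.

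**The case against.** The strongest reply is that the analysis that matters is not short of power. Sections 10.4 and 11.2 make the all-abdominal set primary and the v8.0 subset secondary. At 66 subjects every component criterion has at least 93% power, and at 56 evaluable at least 87%. This stands, and it limits the point: the component shortfall is confined to the 44-subject set. Section 11.2 nevertheless makes its claim for both.

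A second reply is that estimating a single-arm composite while testing its components is a legitimate design, and that Section 10 leaves detail to an SAP to be finalised before database lock. That also stands. The fault is the claim of power for an endpoint that is only estimated.

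Three stronger readings are tempting, and the documents do not support them.

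- A reader might take 58% as the power of the primary endpoint. It is the chance of meeting three group-level criteria together, under a rule that the plan does not contain, with independence and an exact CI assumed.
- A reader might multiply P(60 to 100 mmHg) = 82.3% under a normal distribution (mean 80.2, SD 14.8) by 85% and conclude that CCS cannot exceed 70%. That product is a ceiling only under independence or negative dependence; otherwise the bound is 82%. Seal loss could affect both pressure and leakage, so positive dependence is plausible. The calculation also treats 14.8 as the spread of subjects' average pressures, which Section 11.1 does not spell out.
- A reader might infer that success must mean all three criteria in the full analysis set. Section 10.2 asks for both the full and the per-protocol sets, and a conjunctive rule is a design choice the plan has not made.

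**Conclusion.** The power statement is wrong as written, in two respects. For the composite, no calculation supports it at either sample size, and none is possible without a benchmark. For the 44-subject set it also fails at component level: the specified TOST has 73% power with all 44 evaluable and 62% with the planned 38, against the stated 80%. This second result uses only the plan's SD, margin, alpha and zero true difference, with 14.8 taken as the SD of subject means, as the plan's own calculation does. It does not depend on the CI method for exudate or on how the components are related, because the chance of meeting all criteria cannot exceed the chance of meeting the weakest.

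The primary 66-subject analysis is adequately powered on its components. The documents give no ground for calling the trial as a whole underpowered.

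**What to change.** - In Section 11.2 and the synopsis, limit the power claim to the component tests in the 66-subject abdominal analysis.
- For the 44-subject v8.0 set, state TOST power as 73%, or 62% with 38 evaluable.
- In Section 11.1, correct the figure of 38 for 80% power: under the specified TOST, 38 gives 62%, and 80% needs 49 evaluable.
- In Sections 10.4.1 and 11.2 and the SAP, state that CCS is estimated, neither tested against a benchmark nor powered. Give the expected precision: a 95% CI of about 12 points either side at 66 and 14 at 44 if CCS is near 70%, labelled as an assumption.

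The cost is wording and a less favourable stated power for the secondary analysis. No extra subjects, visits or data are needed.

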**9.1.3 Baseline Operative Visit (Within 6 weeks of screening)**

NOTE: Any subject who has signed an informed consent but at this visit no longer meets the required eligibility criteria prior to the study dressing application is considered to be a Screen Failure. Information must be captured in the appropriate CRFs up to the point of screen failure with the reason for screen failure specified (section 7.4).

1. Query subject regarding any changes in general health and the use of concomitant medications (if screening and surgery are not on the same date).
2. Commence operation and collect surgery data [e.g. Type of surgery (closed surgical incision, (type of abdominal surgery, type of knee surgery, incision length, anatomical location and method of closure),
3. Collect surgery risk factors (elective/emergency surgery, laparoscopic (y/n), incision length, use of prophylactic antibiotics, type (single/double/triple

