## CONFIDENTIAL AND PROPRIETARY

This document contains information that is confidential and proprietary to Smith & Nephew PLC and Smith & Nephew, Inc. and is intended for use only by Smith & Nephew and its manufacturer. It shall not be reproduced or copied in whole or in part, nor shall the contents be disclosed by any means without prior written permission from Smith & Nephew, nor shall anyone make any use of it that is contrary to the expressed or implied wishes of Smith & Nephew.

\_\_\_\_\_ - \_\_\_\_\_ - \_\_\_\_\_

**Clinical Protocol - Device****Pre-Registration Clinical  
Study**

Study Number:  
CT1705POB  
Version: 9.0 04Aug2021  
Page: 65 of 221

agent) and when administered (prior to start of surgery/after surgery began), shaving of incision (yes/no/not needed), use of a wound protector (yes/no), surgical bioburden level(clean/clean-contaminated/contaminated/dirty), intraoperative warming (yes/no))

4. Confirm eligibility following surgery details. NOTE: Subjects that no longer meet the eligibility criteria following surgery will be deemed a screen failure; operative information must be captured in the appropriate CRF with the reason for screen failure specified. These subjects will be replaced.
5. Photograph incision using the camera ( [REDACTED] ) provided by the Sponsor.
6. Assess the incision characteristics for likelihood of SSC (oedema, seroma, haematoma, skin necrosis).
7. Assess the surrounding skin including the area under the pump (e.g., healthy, fragile, inflamed, erythema, bruising, eczematous, dry/flaky, macerated).
8. Dispense study product. Record pump lot number, size of dressing used [REDACTED] and any ancillary products applied (SECURA No-Sting Skin prep, RENASYS Adhesive Gel Patch). Record also ancillaries in the vicinity (e.g. drains, stomas, lines, dressings).
9. Assess ease of application, ease of establishing seal/negative pressure delivery, satisfaction of applying IP.
10. Take photograph of dressing in place. Take a photograph of the carton label to aid accountability checks (the label will contain the batch number).
11. If any adverse device effects or device deficiencies are observed or reported, they must be recorded as instructed in Section 12 - Adverse events and device deficiencies.
12. If there were failed attempts at applying the study product. Please record the device details and disposition of the device.

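### Sections 10.4.1 and 10.4.2 use single-factor significance on the same data to decide which baseline factors are eligible for the final logistic models, so inference on any selected factor is not valid

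*Combined protocol and SAP*

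**What the plan says.** Section 10.4.1 plans un-adjusted and adjusted logistic models for CCS. Three covariates are fixed in advance: those "to be included in the final model are Age, Diabetic status and the presence of any other co-morbidity". The rule for everything else has two parts. First, "All other baseline and medical factors collected at baseline will be evaluated for importance in adjusted models". Second, "only those statistically significant in an un-adjusted model will be considered in the final model". Section 10.4.2 repeats the rule for surgical site infection (SSI) and surgical site complications (SSC).

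No significance level is attached to the screen. The only general statement is in section 10.1: "The results will be reported at 5% significance level". The candidate pool is open. Section 10.3 describes baseline variables that "include but are not limited to age, gender, ethnicity, medical and medication history, diagnostic factors", and section 9.1.3 adds a long operative list, beginning "Collect surgery risk factors (elective/emergency surgery, laparoscopic (y/n), incision length, use of prophylactic antibiotics" and continuing with items such as "shaving of incision (yes/no/not needed), use of a wound protector (yes/no". Nothing says what happens to a factor once it has been considered.

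The abdominal cohort is the main analysis group. Section 11.2 says: "This will increase the total number of abdominal incisions to 66".

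**The concern.** Choosing covariates by their p-values and then reporting p-values and intervals from the same data ignores the selection step. Among many unrelated factors, some will pass by chance and carry that chance result into the final model. Factors that pass tend to be those whose estimates happened to be large, so the reported odds ratios are too far from 1. A real but modest predictor usually fails the screen and is dropped.

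Sections 10.1 and 10.4 look to regression models, alongside descriptive analysis, to deal with confounding in a non-randomised study. A factor reported from these models as associated with device success, infection or complications would carry more apparent certainty than the data give. Section 10.4 also requires the analyses in FAS and PP and in the post-interim subsets s-FAS and s-PP, so there are several overlapping chances for a spurious association to appear.

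**Working it through.** The documents give no figure for covariate selection, so there is no planned value to reproduce.

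**Inputs**
- Screening level: 5%, assumed from section 10.1.
- Subjects: 66 abdominal (section 11.2), 44 in the post-interim subset.
- Forced covariates: 3 (section 10.4.1).
- Candidate factors: not stated. Sections 9.1.1, 9.1.3 and 10.3 name roughly 25 to 29 beyond the forced three: sex, ethnicity, vital signs, substance use, surgery type, site, closure, approach, incision length, antibiotic use, type and timing, shaving, wound protector, bioburden, warming, four incision signs, skin condition, dressing size, ancillaries and others. Some are constant or nearly so (surgery is elective by inclusion criterion), which leaves about 20 to 25 usable. This is my count.
- CCS rate: not stated; 50%, 70% and 85% are assumed.

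**Step 1: nominal chance that at least one of k independent noise factors passes**

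P = 1 − (1 − 0.05)^k
- k = 10: 40.1%
- k = 14: 51.2%
- k = 20: 1 − 0.95^20 = 64.2%, with 20 × 0.05 = 1.0 factor expected to pass
- k = 25: 72.3%
- k = 30: 78.5%

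This formula does not contain the sample size.

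**Step 2: simulation of the rule**

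Twenty independent noise factors were used, 75% binary (prevalence 10% to 50%) and 25% continuous, with 500 runs per setting (Monte Carlo error about ±4 points). Each factor was screened alone. Those passing the Wald screen were then fitted jointly with three forced covariates. All percentages are of all simulated trials.

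| n | CCS rate | At least one passes, Wald | At least one passes, likelihood ratio | At least one still p<0.05 in final model (Wald) |
|---|---|---|---|---|
| 66 | 50% | 54% | 71% | 46% |
| 66 | 70% | 55% | 70% | 49% |
| 66 | 85% | 42% | 67% | 35% |
| 44 | 50% | 53% | 72% | 45% |
| 44 | 70% | 51% | 71% | 41% |
| 44 | 85% | 39% | 72% | 27% |

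With 20 correlated factors (latent correlation 0.2, n = 66, CCS 70%) the three results are 50%, 64% and 39%.

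**Step 3: effect on a real predictor**

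A continuous factor with a true odds ratio of 1.5 per SD was simulated at n = 66 and CCS 70%. It passes the Wald screen in 28% of trials. Among those trials the median estimated odds ratio is 2.1.

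**Step 4: events available**
- CCS failures at a 70% rate: 66 × 0.30 = 19.8. At 85%: 66 × 0.15 = 9.9.
- SSCs at the 8.2% abdominal rate quoted in section 9.2.1: 66 × 0.082 = 5.4, or about 5.

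The three forced covariates alone are already demanding for SSC, before any screened factor is added.

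**The case against.** The strongest reply is that the text does not admit every significant factor. Un-adjusted significance makes a factor eligible to be considered, and factors are also to be evaluated in adjusted models. That stands. A reader might infer that a noise factor has a 64% chance of ending up in the final model; the documents do not support this. The 64% is the nominal chance of passing the screen. If adjusted significance is also required, the simulated figure is about 35% to 49%, below even odds.

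A reader might also blame the sample of 66. The nominal figure does not depend on it, and Wald tests in small samples lower the chance of passing.

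The factor count is open to dispute. ASA is restricted to 2 or 3, antibiotic type and timing are nested within antibiotic use, and dressing size and ancillaries may not be baseline factors. Even with 14 independent factors, however, the nominal figure is 51%.

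The trial is single-arm, so selection cannot distort a treatment contrast. It would be wrong to infer that the main performance results are compromised: CCS is reported as a count and percentage with a 95% interval, and the pressure, wear-time and leakage analyses do not use this model. No section says the model will define who should receive the device.

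Finally, section 10 promises a more detailed SAP before database lock. That could supply a candidate list and retention rule, but the problem here is a stated rule and not only missing detail. A SAP that carried it forward would keep the defect.

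**Conclusion.** The concern holds for the adjusted models only. As written, the rule bases eligibility on single-factor significance in the same data, over an open pool of factors. P-values and confidence intervals for selected factors are not valid, and selected odds ratios are inflated.

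The size rests on three assumptions: a 5% screen, about 20 usable unrelated factors, and CCS rates between 50% and 85%. Under these, the chance that at least one noise factor passes is 64% nominally and about 42% to 55% in simulation with Wald tests at n = 66 (about 67% to 71% with likelihood-ratio tests). The figure for remaining at p<0.05 in the final model further assumes that all screened factors are fitted jointly with the three forced ones, a step the protocol leaves open. The rule should be replaced before the SAP is final.

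**What to change.** In both 10.4.1 and 10.4.2, delete the whole sentence that ends with the screening condition. Fit the adjusted models with only the three covariates already named. Use Firth-penalised logistic regression where events are few, as expected for SSC (about 5 events at the quoted rate) and possible for CCS if its rate is high.

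Report all other baseline factors as unadjusted odds ratios with 95% confidence intervals, in one table labelled exploratory, with no selection. The label matters: with 20 unrelated factors there is still a nominal 64% chance that at least one interval excludes 1, but the full table lets the reader see how many were examined.

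The cost is wording in the protocol and SAP. The small downside is that an unanticipated predictor would appear only in the exploratory table.
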